Power analysis and estimate of sample size for Experiment 1 [name] (our biostatistician consultant) has performed power analysis based on our pilot study and historical data from the literature. A two-way repeated measures ANOVA was used to determine whether any change in VAS score was due to the interaction between INTERVENTION and TIME (i.e. whether one of two interventions is more effective at reducing VAS scores). A power analysis using the G*power computer program (Faul et al. 2007) indicated that a sample of 12 people would be needed to detect a large effect size (> 0.8) with 85% power using a repeated measures two-way ANOVA with alpha at .05, a sample of 14 people would be needed for 90% power. To account for possible subject withdrawal (10%), we plan to recruit 16 subjects. Also to reduce the experimental bias and the order effect, the order of the interventions will be randomized.

Pilot data and sample size for Experiment 2 (Aim 2)

In Experiment 2, the same BreESTim protocol will be used, but at two different doses (120 stimuli vs. 240 stimuli). We have tested the protocol in 4 patients with phantom limb pain after BKA (Figure 5). On average, BreESTim120 and BreESTim240 had similar analgesic effects. VAS decreased from 6.4 to 3.5 after BreESTim120, and from 5.9 to 3.5 after BreESTim300. However, the analgesic effect lasted longer after BreESTim240 (26.1 hours) than after BreESTim120 (14.5 hours). Similar to Experiment 1, these data are from IRB approved study MS-20-1032

analgesic effects were paralleled with similar degrees of change in EPT without changes in other thresholds.

[figure not shown]

[figure not shown]
Figure 5 BreESTim has a dose-response effect on the duration, not the degree of analgesic effects on phantom limb pain.

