Power analysis and estimate of sample size for Experiment 3 [name] (our biostatistician consultant) has performed power analysis based on our pilot study and historical data from the literature. Using nQuery Advisor®, we applied the t-test (ANOVA) for difference of VAS in 2 x 2 crossover design with a 0.05 two-sided significance level. To achieve 80% power of detecting a difference in VAS of 3.0 (the difference between the mean of group BreESTim, $\mu_1=4.0$ and the mean of EStim group, $\mu_2=2.0$) assuming that the Crossover ANOVA \sqrt{MSE} is 3.4 (the Standard deviation of differences, σ_d , is 4.8), the sample size is 24. Assuming an expected dropout rate of 20% given the long-term intervention, we proposed to recruit 30 patients in total for Experiment 3.

D. The data collection and measurement techniques are appropriate and effective

- **Experimental Design**

The overall research design is a within-group, randomized controlled study to compare analgesic effects between EStim and BreESTim (single-session in Exp 1, long-term intervention in Exp 3), between BreESTim120 and BreESTim240 (Exp2). We prefer this within-group comparison because 1) pain, by nature, is a subjective perception, it is difficult to control (physical, social, psychological) multi-factors between two groups; 2) It will be fair that all subjects receive the innovative intervention, which is superior to regular electrical stimulation according to our pilot data; 3) according to our recent BreESTim study in patients with spinal cord injury, the duration of analgesic effect was 15 hours after one-session of BreESTim treatment. An interval of one week for washout should be sufficient for Exp 1 & 2. The washout interval will be 2 weeks for Exp 3. It is our experience with subjects with spinal cord injury that an interval of 7 days is sufficient for subjects to return to their baseline after BreESTim treatment. (Li et al. 2016; Karri et al. 2018b; Li et al. 2018) However, we did notice that one subject with post-amputation PLP had carry-over effect for one month(Li et al. 2012a). We plan to screen these patients with long-lasting carry-over effects. These patients will be excluded from the subject should this happen.

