Experiment 2 Similar to Exp 1, repeated-measures two-way ANOVA tests with factors INTERVENTION (2 levels, BreESTim 120 vs. 240) and TIME (pre- and post-intervention) will be tested on dependent variables, including VAS, QST thresholds (tactile, electrical, and thermal), to determine statistical significance between two interventions. Paired t-tests will be used to compare the duration of analgesic effect (lasting hours) between two interventions. p value is set at 0.05. As shown in the pilot data, we expect that BreESTim could have dose-dependent effects on the duration but not the degree of analgesic effects. These results also suggest that BreESTim could have cumulative effects if patients receive interventions repeatedly over a period of time.

In Experiment 3, Repeated-measures two-way ANOVA will be performed to determine statistical significance between two interventions. Factors include INTERVENTION (BreESTim vs. EStim) and TREATMENT (Pre- and Post-intervention, and Followup). Variables are VAS and modified VAS and QST parameters, GWB, and CES-D. It is hypothesized that the effect of pain reduction is greater in BreESTim than in EStim for amputation patients, manifested by pain reduction on VAS assessment and parallel change of increased electrical pain threshold as shown by pilot data in Experiments 3. Furthermore, pain reduction is accompanied by improvement in general well-being and mood.

Demographic data will be analyzed descriptively. Personal information will be de-identified. HSC-MS-20-1032

7. Potential Risks/Discomforts:

The risks associated with this study are minimal. Electrical stimulation has been used extensively in clinical settings. Patients may feel uncomfortable, or even painful during electrical stimulation. The patients will be specifically instructed that they are encouraged to increase the intensity of electrical stimulation to the level they may feel comfortable, but they need to be able to tolerate at that level if given repetitively. They are also explicitly instructed to decrease the intensity of electrical stimulation if they can not tolerate it. Surface electrodes can cause skin irritation from the tape adhesive or the electrode paste. Breathing through a face mask may be make patients feel uncomfortable. All tested subjects in the previous studies (approximately 100 subjects, including patients) tolerated the mask well.

8. Benefits:

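### Experiment 3 expects 20% dropout, but its repeated-measures ANOVA in standard form drops a patient from an outcome's analysis when any one of six values is missing, and no rule covers incomplete patients

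*Combined protocol and SAP*

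**What the plan says.** Section 4, part C, sizes Experiment 3 as a 2 x 2 crossover "with a 0.05 two-sided significance level". The aim is stated as "To achieve 80% power of detecting a difference in VAS of 3.0". With a root mean square error of 3.4 and a standard deviation of differences that "is 4.8), the sample size is 24". It then adds: "Assuming an expected dropout rate of 20% given the long-term intervention, we proposed to recruit 30 patients in total for Experiment 3". The Experiment 1 paragraph makes a smaller allowance: "To account for possible subject withdrawal (10%), we plan to recruit 16 subjects".

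Section 6 gives the Experiment 3 analysis: "Repeated-measures two-way ANOVA will be performed to determine statistical significance between two interventions". The layout follows: "Factors include INTERVENTION (BreESTim vs. EStim) and TREATMENT (Pre- and Post-intervention, and Followup"). It applies to VAS, modified VAS, QST, GWB and CES-D. Experiments 1 and 2 use the same kind of ANOVA with pre and post only, plus paired t-tests for duration of effect.

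The expected losses are used only to raise recruitment. The text available to me has no analysis population, missing-data rule, mixed model, imputation or sensitivity analysis. I could not see the Experiment 2 sample-size paragraph. Section 13 pays for Experiment 3 on completion of all 20 sessions, as a retention measure.

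**The concern.** A two-way within-patient ANOVA in its usual form needs a full row for every patient. In Experiment 3 a row is 2 x 3 = 6 values per outcome. A patient who completes all 20 sessions but misses the last follow-up VAS is removed from the VAS analysis, although five valid values exist. A patient who stops after the first course contributes nothing to the comparison.

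Two things are at stake. One is precision: missed values among patients who stay are not covered by the extra recruitment. The other is bias: if patients with little relief in period 1 are less likely to return, the completers are a selected group. The plan expects little or no change in pain after EStim (Section 4, part D), so on its own hypothesis such losses would fall more on patients given EStim first. Completers' EStim results would then look better than they were, and the difference between interventions would shrink.

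**Working it through.** **1. The plan's sample size.** Inputs from Section 4, part C: two-sided alpha 0.05, difference 3.0, SD of differences 4.8 (3.4 x √2 = 4.81). With a noncentral t on n - 2 degrees of freedom, the smallest n for 80% power is 23, or 24 with equal sequences. At n = 24 the noncentrality is 3.0 x √24 / 4.8 = 3.06 and power is 83%. Inflation: 24 / 0.80 = 30 and 14 / 0.90 = 15.6, rounded up to 16. Both agree with the plan. If 24 of 30 complete, power for 3.0 is intact.

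**2. Single missed values among the 24 who stay.** Assume each of the six values is missed independently with probability q. Complete rows = 24 x (1 - q)^6.

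| q (assumed) | complete rows | power for 3.0 |
|---|---|---|
| 1% | 22.6, about 23 | 82% |
| 2% | 21.3, about 21 | 78% |
| 5% | 17.6, about 18 | 70% |
| 10% | 12.8, about 13 | 54% |

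**3. Bias, by formula.** Assume no between-patient spread, period results with SD 3.4, a true difference of 3.0, and dropout after period 1 whenever the reduction falls below one cut-off c, chosen so that 20% leave overall. This gives c = -1.65.

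- BreESTim first: z = (-1.65 - 3.0)/3.4 = -1.37, so 8.6% leave.
- EStim first: z = -1.65/3.4 = -0.48, so 31.4% leave.
- The completers' period-1 mean rises by 3.4 x φ(z)/(1 - Φ(z)): 0.58 and 1.76 respectively.
- Completers' difference = [0.914 x (3.0 + 0.58) + 0.686 x (3.0 - 1.76)] / (0.914 + 0.686) = (3.272 + 0.851)/1.600 = 2.58.

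With no true difference both sequences lose 20%, both shifts are 1.19, and they cancel to zero.

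**4. Bias, by simulation of 30 patients.** Here the six worst period-1 responders leave. Assumed within-patient SD is 2.0 to 3.4 and between-patient SD 1 to 2. Both 2.0 and 3.0 are used as true values because the sample-size paragraph names a difference of 3.0 but gives means of 4.0 and 2.0.

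| true difference | completers only | likelihood fit, all observed data |
|---|---|---|
| 2.0 | 1.73-1.86 | about 2.0 |
| 3.0 | 2.60-2.81 | about 3.0 |

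The shortfall is about 6-13%. Of the six who leave, about 4 to 5 had EStim first.

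**5. Other mechanisms (20% dropout, within-patient SD 3.4, between-patient SD 0 to 3.4).** Completely random dropout gives no bias. If poor response only raises the chance of leaving, a true 3.0 becomes 2.78-2.87. If only EStim-first patients leave (40% of that sequence), it becomes 2.18-2.44, and a true zero becomes about -0.6 to -0.8, that is, against BreESTim.

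**6. Which mixed model.** A random patient intercept alone does not stand in for the planned ANOVA. With patient-by-intervention and residual SDs both 1.5 (assumed), the patient-by-intervention mean square is 2.25 + 3 x 2.25 = 9.0 on n - 1 degrees of freedom, and the other within-patient terms are 2.25 on 4(n - 1). Pooled, this is (9.0 + 4 x 2.25)/5 = 3.6, and 3.6/2.25 = 1.6 times the ANOVA's interaction error. A patient-by-intervention random effect removes this. Period also matters: with unbalanced dropout and an assumed period effect of ±1 VAS point, a fit without period gave 2.88-3.12 for a true 3.0, and a fit with period gave 2.96-3.05.

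**The case against.** The strongest reply is that the plan has dealt with withdrawal: it recruits 30 for 24, which holds 83% power for its stated difference, and Section 13 ties payment to completion. This stands for the expected withdrawals. It does not reach missed values among stayers or selective loss, and the plan still expects 20% to leave.

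The bias is also modest and rests on an assumed mechanism; the documents do not say why patients would leave. With the six worst responders leaving, it is about 0.1 to 0.4 VAS points, against a standard error of 4.8/√24 = 0.98. That stands, and it is why this is a recommended change and not a fatal flaw. The plan also excludes patients with long carry-over, a selection on strong and lasting response that these calculations leave out.

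Three stronger readings are tempting and not supported:

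- A reader might infer that one missed follow-up discards everything a patient contributed. Deletion is per outcome: a missing follow-up VAS leaves that patient's QST, GWB and CES-D analyses untouched. Experiments 1 and 2 have no follow-up level; there the loss comes from a missed pre or post value or a missed second visit.
- A reader might infer that the analysis will favour BreESTim or produce false positives for it. In every outcome-dependent scenario with a true difference, the bias ran against BreESTim. With no true difference and one rule in both sequences, it was about zero.
- A reader might infer that withdrawals will go unreported. The documents do not say so.

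**Conclusion.** The point holds for Experiment 3. Dropout of 20% is expected, the named analysis in its standard form uses complete rows only, and no rule says otherwise. The plan does not state a complete-case analysis; that follows from the method it names.

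The size depends on assumptions that the documents cannot settle. Loss of the six worst first-period responders makes the difference about 6-13% too small, and loss confined to the EStim-first sequence makes it worse. Independent gaps of 5% per value among the 24 who stay would cut power from 83% to about 70%. If dropout is completely at random and stayers miss nothing, neither problem arises. The change is worth making because it is cheap and the rule should be fixed before data are seen.

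**What to change.** In Section 6, make the primary Experiment 3 analysis a likelihood-based linear mixed model on every observed value from all randomised patients with at least one session. Fixed effects: sequence, period, intervention, time and intervention-by-time. Random effects: patient and patient-by-intervention (period within patient), or an unstructured within-patient covariance if it can be estimated with this many patients. With complete data, the random-effects form gives an interaction test in line with the planned ANOVA. Adding a patient-by-time random effect reproduces the ANOVA's error term if patients also differ in their time course.

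Keep the completers' ANOVA as a sensitivity analysis. Report withdrawals and reasons by sequence and intervention received. Do not enter scores collected after stopping as outcomes of an intervention that was never given. Use the same approach in Experiments 1 and 2 for a missed second visit.

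The cost is revised wording and slightly more analysis work, with no extra patients or visits. The model relies on missing at random, so if dropout depends on unrecorded outcomes some bias can remain.

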In Experiment 1, we plan to use our recent BreESTim and EStim protocols (Li et al. 2013; Li et al. 2014; Li et al. 2016) to measure mechanical sensation threshold, thermal (cold/warm detection, cold/hot pain) thresholds, and electrical sensation and pain thresholds in the treatment limb and contralateral limb. The same group of subjects will receive both BreESTim and EStim at a randomized yet balanced order with at least 7 days apart. The same amount of electrical stimulation (120 stimuli) will be given during both BreESTim and EStim. The purpose of this aim is to investigate whether BreESTim could have better analgesic effect than EStim in amputee subjects with chronic phantom limb pain as we observed in healthy subjects. We expect increased electrical pain thresholds in both limbs after BreESTim because of its central desensitization effects.

In Experiment 2, a group of subjects will receive BreESTim at two different doses (120 vs. 240 stimuli) on two different days with at least 7 days apart. The purpose is to compare the extent and duration of analgesic effects between two doses of BreESTim. We expect that BreESTim240 could have similar degree of pain reduction but with longer duration compared to BreESTim120, as shown in our pilot study. Therefore, we expect to use BreESTim240 in Experiment 3 for the long-term intervention.

[figure not shown]

Figure 7: Illustration of study design for Experiments 3

In Experiment 3, the same established protocol will be used (Li et al. 2012a; Li 2013). The effect of two interventions (BreESTim and EStim) will be compared. Each intervention consists of 240 stimuli/session (about 40-50 min/session), 1 session/day for 10 consecutive sessions (over 2 weeks). After a follow-up (wash-out) period of two weeks, the same subject will be treated with the other intervention with a same follow up of 2 weeks. The intensity of stimulation will be adjusted as subjects could tolerate. Electrical stimulation will be delivered to the median nerve on the dominant side. The wash-out/follow-up period of 2 weeks allows removal of accumulative or carry-over effect from the previous intervention.

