Experiment 2 The aim of this experiment is to explore this “dose-response” effect of BreESTim, by comparing the analgesic effects of two doses of single-session BreESTim. The same BreESTim protocol in Exp 1 will be used for Exp 2. In Exp 2, only BreESTim will be used. Two doses of BreESTim (120 vs. 240 electrical stimuli) will be given at least one week apart in a randomized order. Outcome measures, including VAS, QST thresholds, will be recorded pre- and 10 minutes post-intervention. Duration of analgesic effect (lasting hours) will also be recorded.

Experiment 3 The experimental set-up will be similar to Experiments 1&2. There are two different interventions – BreESTim and EStim. Each intervention consists of 240 stimuli/session (about 40-50 min/session), 1 session/day for 10 sessions (over 2 weeks, no treatment in the weekends). After a follow-up (wash-out) period of two weeks, the same subject will be treated with the other intervention with a same follow-up of 2 weeks. The intensity of stimulation will be increased gradually as patients could tolerate. Aversiveness of electrical stimulation is part of treatment strategy. During EStim, a single-pulse electrical stimulation is delivered to the forearm through surface electrodes randomly, while electrical stimulation is triggered by volitionally effortful inhalation during BreESTim as in Exp 1.

Specimens:

No specimens will be collected

5. Human Subjects

As mentioned above, we plan to recruit a total of 64 amputee subjects with phantom limb pain, including 16 subjects for Aim 1, 18 subjects for Aim 2, and 30 subjects for Aim 3. The number of subjects was estimated based on the pilot data.

• Subject recruitment/assignment

The collaborating physician (Co-I, [name]) will screen patients from the outpatient clinic of TIRR Memorial Hermann Hospital. We plan to register the project on www.clinicaltrials.gov. If patients are not currently seen by [name], but are willing to participate in the project, they need to see [name] for screening and monitoring. In addition, [name] will monitor medical conditions of the patients and manage medical problems as needed. Patients will be recruited and enrolled in the project if they meet the following criteria:

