There are several potential benefits in this study: 1) direct benefit to subjects as their neuropathic pain may be relieved by the intervention; 2) benefit to the class of subjects: other patients in the same patient population may be benefit if the intervention is applied to them; 3) adding to the knowledge base: the findings will be definitely added to the knowledge base. Specifically, the study will provide evidence of an alternative and innovative intervention for neuropathic pain management after amputation.

9. Risk-benefit Ratio:

In view of the minimal risk, the knowledge to be gained far outweighs the risks.

10. Consent Procedures:

Informed consent will be obtained from the subject. After the subject is identified and is interested in participating, informed, written consent will be obtained by the investigator.

11. Confidentiality Procedures:

In order to minimize risk to confidentiality, all data will be de-identified, coded with a study-specific identification number, maintained on a password-protected server, and/or kept in a locked office. No findings will be released without written authorization by the subject or requests by law.

12. Costs:

The subject will not be expected to pay any costs.

13. Payments:

Subjects will receive a gift card of \$40 for their participation in each session for Experiment 1 and 2. Experiment 3, each subject will have a total of 20 sessions (10 consecutive sessions of BreESTim, and 10 consecutive sessions of EStim, with 2 weeks apart). Each subject will receive a giftcard of \$40 after the first session. Each of them will receive a total of \$800 after the completion of all 20 sessions. No monetary compensation will be given if 20 sessions are not completed. This is to keep commitment and for subject retention.

14. References:

Adams, P. F., Hendershot, G. E., Marano, M. A. (1999) Current estimates from the National Health Interview Survey, 1996. *Vital Health Stat* 10,1-203

Alviar, M. J., Hale, T., Dungca, M. (2011) Pharmacologic interventions for treating phantom limb pain. *Cochrane database of systematic reviews (Online)* 12

Aminoff, M. J., Sears, T. A. (1971) Spinal integration of segmental, cortical and breathing inputs to thoracic respiratory motoneurons. *J Physiol* 215,557-575

Apkarian, A. V., Bushnell, M. C., Treede, R. D., Zubieta, J. K. (2005) Human brain mechanisms of pain perception and regulation in health and disease. *Eur J Pain* 9,463-484

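### Experiment 3 is sized on a one-degree-of-freedom crossover test, but the planned 2 x 3 ANOVA names no deciding contrast and has no period or sequence term

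*Combined protocol and SAP*

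**What the plan says.** **Sizing.** Section 4, part C (power analysis for Experiment 3) states: "we applied the t-test (ANOVA) for difference of VAS in 2 x 2 crossover design with a 0.05 two-sided significance level". The inputs are 80% power, a VAS difference of 3.0, root MSE 3.4 and SD of differences 4.8. This gives 24 patients, raised to 30 for 20% dropout.

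**Analysis.** Section 6, Experiment 3 states: "Repeated-measures two-way ANOVA will be performed to determine statistical significance between two interventions". The factors follow: "Factors include INTERVENTION (BreESTim vs. EStim) and TREATMENT (Pre- and Post-intervention, and Followup"). The dependent variables are VAS, modified VAS, QST parameters, GWB and CES-D. The hypothesis has a direction: "It is hypothesized that the effect of pain reduction is greater in BreESTim than in EStim for amputation patients". No model term or visit is attached to it.

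**The only term named for any test** is in the Experiment 1 sizing, where the ANOVA was used "to determine whether any change in VAS score was due to the interaction between INTERVENTION and TIME". Experiment 1 has two time points.

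**Design.** Section 4, part D describes two treatment periods: "After a follow-up (wash-out) period of two weeks, the same subject will be treated with the other intervention". Section 13 confirms the spacing: "10 consecutive sessions of BreESTim, and 10 consecutive sessions of EStim, with 2 weeks apart". The same two weeks serve as follow-up and as washout. Part D supports the washout with a 15-hour effect after one session and a return to baseline by 7 days in spinal cord injury. It also reports one amputee whose carry-over lasted a month, and says that patients with long carry-over will be screened and excluded, without saying when.

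**The concern.** A 2 x 3 repeated-measures ANOVA produces several tests of the intervention. The main effect averages over all three visits, including the one before treatment. The interaction asks whether the between-intervention difference varies at all over the three visits. A pre-to-post contrast asks whether pain fell more by the end of treatment. These are different questions with different power, and only the last matches both the hypothesis and the sizing. With no contrast named, the stated 80% power attaches to none of them for certain, and the test can be chosen after the data are seen.

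The design is also a two-period crossover analysed without period or sequence. Whether that matters depends on which test decides and on how a period effect acts. Carry-over is a separate matter, because the visit that ends the washout is also the baseline for the second intervention.

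**Working it through.** All tests are two-sided at 0.05. N = 24, difference 3.0 and SD 4.8 come from the Experiment 3 sizing. Share of benefit kept at follow-up, correlation between visits, period effect and residual benefit are assumptions.

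**1. The plan's figure.** 3.4 x √2 = 4.81, so the two stated SDs agree. Noncentrality = 3.0 / (4.8/√24) = 3.06. With 22 df (crossover), power is 83.3%; 22 patients give 79.6%, so 24 is the smallest even number reaching 80%. 24 / (1 − 0.20) = 30. The stated size reproduces.

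**2. Which test?** Let the BreESTim minus EStim differences at pre, post and follow-up be (0, 3, 3f), with f the share kept.
- *Interaction:* λ = N Σ(d − d̄)² / (SD²/2), where SD = 4.8 is the SD of the difference in change and SD²/2 = 11.52, on F(2, 46). For f = 0 or 1, Σ = 6 and λ = 24 x 6 / 11.52 = 12.5. For f = 0.5, Σ = 4.5 and λ = 9.375.
- *Main effect:* the mean difference is 1.0, 1.5 or 2.0. Its SD is 4.8 x √((1 + 2ρ)/3), which is 3.92 at ρ = 0.5, on 23 df.

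At ρ = 0.5 an SD of 4.8 at each visit implies an SD of change of 4.8 x √(2 x 0.5) = 4.8, so the columns compare directly.

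| Kept at follow-up | Pre-to-post contrast | Interaction, 2 df | Main effect |
|---|---|---|---|
| 0% | 83% | 87% | 22% |
| 50% | 83% | 76% | 44% |
| 100% | 83% | 87% | 67% |

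If 4.8 is the SD at each visit and ρ runs from 0 to 0.7, simulated power is 46 to 98% for the interaction and 20 to 93% for the main effect.

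λ uses squared deviations, so reversing the sign of every difference leaves the interaction's power unchanged. A significant F does not say which intervention is better, or at which visit.

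**3. Omitted period term.** A shift common to all visits of a period drops out of change from pre to post, and out of the interaction. It can move the main effect when sequences are unequal. Suppose instead that the change itself differs by π between periods. The two sequences then have mean differences 3.0 − π and 3.0 + π.
- *12 and 12 completers:* no bias, but π enters the error. The residual sum of squares over 4.8² is noncentral chi-square on 23 df with noncentrality 24π²/4.8² (1.04, 4.17, 9.38 for π = 1, 2, 3). Power is 82%, 79% and 73%.
- *10 and 14 completers:* bias = π x (14 − 10)/24 = 0.17π, or 0.17, 0.33 and 0.50 points.

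**4. Carry-over.** Let L be the net residual BreESTim benefit at the start of period 2. If it fades by the end of that period, patients given BreESTim first start EStim L points lower, and their EStim reduction is understated by L. The other sequence is unaffected, so the average contrast is inflated by L/2. If L persists equally through period 2, it cancels. A period term does not remove it.

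**5. Effect of the conflicting means.** The sizing paragraph gives means of 4.0 and 2.0, which differ by 2.0. At 2.0 the contrast has noncentrality 2.04 and 50% power, and the interaction 41 to 52%.

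**The case against.** The strongest reply is that the interaction is plainly meant: the hypothesis concerns greater reduction, and Experiment 1 names that term. On the figures above it costs little, and in two of the three patterns it beats the sized test. That is fair on power. But it is an inference from another experiment with two time points, where the interaction has one degree of freedom and equals the pre-to-post contrast. With three visits it has two, no direction, and is not the test that was sized.

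A reader might infer more than the documents support:
- **That omitting period biases the efficacy result.** A shift common to a period cancels from the natural contrast. The figures in step 3 need a period effect on the change itself, and 3 points equals the whole planned difference. Entry requires stable medication, and the background section says phantom pain does not change after six months, which argues against large effects.
- **That carry-over raises the type I error.** If BreESTim leaves a residual benefit because it works, there is no true null. The result is an inflated estimate.
- **That the washout is unsupported.** Part D gives reasons for it; the one-month case is a single patient.
- **That the exclusion rule certainly selects on response.** Screening could mean before treatment. The text does not settle it.

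Text just before the Experiment 3 sizing was missing from the copy read. It can be said only that the available text gives no period or carry-over figure.

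**Conclusion.** The point stands. The sized test and the planned analysis differ, no contrast is named to decide efficacy, and period and sequence are absent from the model. The main consequence is that power runs from about 22% to 87% at ρ = 0.5 depending on a choice the plan leaves open, and that one candidate test cannot show direction. This rests on the difference of 3.0, on reading 4.8 as step 2 does, and on the assumed share kept. The quoted means of 4.0 and 2.0 fit the hypothesis only as reductions, which favours reading 4.8 as the SD of the difference in change.

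It does not follow that 24 is the wrong number: it is right for the crossover test at 3.0. The conflict between 3.0 and the quoted means affects power more than the switch from the contrast to the interaction does, and must be resolved separately. The period and carry-over sizes are conditional illustrations, not estimates for this trial. The change should be made before analysis, but the point does not invalidate the design.

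**What to change.** - **Primary analysis, Experiment 3:** a linear mixed model with VAS change from pre to end of the ten sessions in each period as the response; intervention, period and sequence as fixed effects and patient as random effect; all available data, including period-1 data from dropouts.
- **Primary contrast:** BreESTim minus EStim from that model, as the only primary test, with the stated power tied to it. Modified VAS (reduction x hours), follow-up and the other variables become secondary.
- **Carry-over sensitivity analysis:** the same contrast from period 1 only, adjusted for baseline. It is imprecise: before any gain from that adjustment, 15 against 15 has about 65% power for 3.0 if the one-period SD is 3.4, and 38% if it is 4.8.
- **Exclusion:** state when the carry-over exclusion applies. Do not drop patients from the analysis set for carry-over found after treatment, since that selects on response.
- **Experiments 1 and 2:** add period to the models.

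**Cost.** One or two degrees of freedom and a little more analysis; no patients. With no period effect, Experiment 3 power goes from 83.4% (23 df) to 83.3% (22 df). Experiment 1, with 16 patients and a standardised effect of 0.8, goes from 84.8% to 84.5%. The two-period contrast still carries any carry-over bias, and keeping patients with long carry-over leaves that bias in. The sensitivity analysis can expose it but not remove it.
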